14 REGISTRATION GUIDELINES

Study related screening procedures can only begin once the patient has signed a consent form.

Patients must meet all of the eligibility requirements listed in [Section 5](#) prior to registration.

Patients must be registered before receiving any study treatment and must be registered within five working days after registration.

To register eligible patients on study, complete a Clinical Trials Office Patient Registration Form and submit to [contact].

15 DATA SUBMISSION SCHEDULE

The Case Report Forms (CRFs) are a set of (electronic or paper) forms for each patient that provides a record of the data generated according to the protocol. CRF's should be created prior to the study being initiated and updated (if applicable) when amendments to the protocol are IRB approved. These forms will be completed on an on-going basis during the study. The medical records will be source of verification of the data. During the study, the CRFs will be monitored for completeness, accuracy, legibility and attention to detail by a member of the Research Compliance Office. The CRFs will be completed by the Investigator or a member of the study team as listed on the Delegation of Duties Log. The data will be reviewed no less than annually by the Data and Safety Monitoring Committee. The Investigator will allow the Data and Safety Monitoring Committee or Research Compliance Office personnel access to the patient source documents, clinical supplies dispensing and storage area, and study documentation for the above-mentioned purpose. The Investigator further agrees to assist the site visitors in their activities.

Data capture should be restricted to endpoints and relevant patient information required for planned manuscripts.

16 ETHICAL AND REGULATORY CONSIDERATIONS

16.1 Human Subject Protections

The study will be conducted in accordance with the appropriate FDA, IRB, ICH GCP and other federal and local regulatory requirements, as applicable. Informed consent will be obtained from all research participants prior to performing any study procedures using the most recent IRB-approved version. All patients must be at least 18 years of age to participate.

16.2 Institutional Review

Before study initiation, the investigator must have written and dated approval/favorable opinion from the IRB/IEC for the protocol, consent form, subject recruitment materials (e.g., advertisements), and any other applicable patient-facing documents. The investigator should also provide the IRB/IEC with a copy of the Investigator Brochure or product labeling information.

The investigator or designee should provide the IRB/IEC with reports, updates and other information (eg, expedited safety reports, amendments, and administrative letters) according to regulatory requirements or institution procedures.

16.3 Data and Safety Monitoring Plan

A Data and Safety Monitoring Committee (DSMC) is established at Huntsman Cancer Institute (HCI) to ensure the well-being of patients enrolled on Investigator Initiated Trials that do not have an outside monitoring review. The roles and responsibilities of the DSMC are set forth in the NCI-approved Data and Safety Monitoring (DSM) plan. The activities of the committee include reviewing adverse events (including SAEs), deviations, important medical events, significant revisions or amendments to the protocol, and approving cohort/dose escalations. If the DSMC and/or the PI have concerns about unexpected safety issues, the study will be

stopped and will not be resumed until the issues are resolved. The DSMC also reviews and approves audit reports generated by the Research Compliance Office.

This is a Phase II treatment study with no IND application classified as moderate risk per the NCI-approved DSM plan.

Each moderate risk study may be assigned a physician member of the DSMC as medical monitor, or in rare cases, an external medical monitor. The medical monitor will be notified of all serious adverse events (SAEs). SAEs occurring in patients treated at HCI or its affiliates will also be reviewed by the full DSMC monthly.

Each moderate-risk study will be assigned a dedicated research compliance officer who will monitor the trial. Moderate-risk trials will be monitored by RCO personnel after the first patient is enrolled and every six months thereafter during active enrollment. The RCO monitor will review the study status and summarize enrollment, toxicities, SAEs, dose escalation, statistical endpoints (e.g., stopping rules), deviations, etc. for the full DSMC membership at the regularly scheduled meetings. Amendments that increase risk, change dosing, or impact study objectives will be reviewed by the DSMC and approved by the PRMC and IRB. Moderate-risk trials will be formally reviewed by the DSMC after the first patient is enrolled and then semi-annually thereafter.

An initial audit of moderate-risk studies will be conducted by the RCO approximately one year after enrollment begins and annually thereafter. Audits of moderate-risk studies may be conducted more frequently as requested by the DSMC, IRB, PRMC, RCO management, or the PI.

16.4 Adverse Events and Serious Adverse Events

This study will utilize the CTCAE (NCI Common Terminology Criteria for Adverse Events) Version 5.0 for AE and SAE reporting.

16.4.1 Adverse Events (AEs)

An adverse event is the appearance or worsening of any undesirable sign, symptom, or medical condition occurring after starting the study drug even if the event is not considered to be related to study drug. For the purposes of this study, the terms toxicity and adverse event are used interchangeably. Medical conditions/diseases present before starting study drug are only considered adverse events if they worsen after starting study drug. Abnormal laboratory values or test results constitute adverse events only if they induce clinical signs or symptoms, are considered clinically significant, or require therapy.

Collection of adverse events will begin from the first dose of study medication and until the end of treatment visit (or until a new cancer treatment is initiated).

Information about all adverse events, whether volunteered by the subject, discovered by investigator questioning, or detected through physical examination, laboratory test or other means, will be collected and recorded and followed as appropriate.

As far as possible, each adverse event should be evaluated to determine:

1. The severity grade based on CTCAE v5.0 (grade 1-5)
2. Its relationship to the study drug(s) (definite, probable, possible, unlikely, not related)
3. Its duration (start and end dates or if continuing at final exam)
4. Action taken (no action taken; study drug dosage adjusted/temporarily interrupted; study drug permanently discontinued due to this adverse event; concomitant medication taken; non-drug therapy given; hospitalization/prolonged hospitalization)
5. Whether it constitutes an SAE

All adverse events will be treated appropriately. Such treatment may include changes in study drug treatment as listed in the dose modification section of this protocol (see section 8 for guidance). Once an adverse event is detected, it should be followed until its resolution, and assessment should be made at each visit (or more frequently, if necessary) of any changes in severity, the suspected relationship to the study drug, the interventions required to treat it, and the outcome.

Information about common side effects already known about celecoxib are described in the Drug Information (section 3) and in the current product insert. This information will be included in the patient informed consent and will be discussed with the patient during the study as needed.

All adverse events will be immediately recorded in the patient research chart.

16.4.2 Serious Adverse Event (SAE)

Information about all serious adverse events will be collected and recorded. A serious adverse event is an undesirable sign, symptom or medical condition which:

- Is fatal or life-threatening
- Results in persistent or significant disability/incapacity
- Is medically significant, i.e., defined as an event that jeopardizes the patient or may require medical or surgical intervention to prevent one of the outcomes listed above
- Causes congenital anomaly or birth defect
- Requires inpatient hospitalization or prolongation of existing hospitalization, unless hospitalization is for:
 - Routine treatment or monitoring of the studied indication, not associated with any deterioration in condition (procedures such as central line placements, paracentesis, pain control)
 - Elective or pre-planned treatment for a pre-existing condition that is unrelated to the indication under study and has not worsened since the start of study drug

- Treatment on an emergency outpatient basis for an event not fulfilling any of the definitions of a SAE given above and not resulting in hospital admission
- Social reasons and respite care in the absence of any deterioration in the patient's general condition

Collection of serious adverse events will begin after the first dose of study medication and end at the end of treatment visit or until a new cancer treatment is initiated, whichever happens the soonest.

Any death from any cause while a patient is receiving treatment on this protocol or up to the end of treatment visit, or any death which occurs more than 30 days after protocol treatment has ended but which is felt to be treatment related, must be reported.

Toxicities which fall within the definitions listed above must be reported as an SAE regardless if they are felt to be treatment related or not. Toxicities unrelated to treatment that do NOT fall within the definitions above, must simply be documented as AEs in the patient research chart.

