9 SCHEDULE OF EVENTS

The Schedule of Events table provides an overview of the protocol visits and procedures. Refer to the Study Procedures section of the protocol for detailed information on each assessment required for compliance with the protocol. The Investigator may schedule visits (unplanned visits) in addition to those listed in the Schedule of Events table in order to conduct evaluations or assessments required to protect the wellbeing of the patient. This Schedule of Events will be followed for the entire study.

Short Title: RESILIENCE

Version Date: 18APR2023

Table 4: Schedule of Events

| Examination | Screening ¹ | Pre-Operation ² | Surgery ³ | Post-Operation ⁴ | 5 Weeks Post-Operation | Mid Radiation ⁵ | End of Treatment ⁶ |
|--|------------------------|----------------------------|----------------------|-----------------------------|------------------------|----------------------------|-------------------------------|
| Informed Consent | X | | | | | | |
| Medical History | X | | | | | | |
| Eligibility Criteria | X | | | | | | |
| Vital Signs | X | | | X | | X | X |
| Physical Exam ⁷ | X | | | X | | X | X |
| Karnofsky Performance Status ⁸ | X | X | | X | | X | X |
| Functional Oral Intake Score | X | X | | X | | X | X |
| Hematology ⁹ | X | | | X | | X | X |
| Chemistry ¹⁰ | X | | | X | | X | X |
| Pregnancy Test ¹¹ | | X | | | | | |
| HIV and Hepatitis Serologies ¹² | X | | | | | | |
| Radiation Oncology Consultation | X ¹³ | | | | | | |
| Surgery | | | X ¹⁴ | | | | |
| Celecoxib/placebo ¹⁵ | | | | X | | | |
| Questionnaires ¹⁶ | | X | | X | | X | X |
| Pre-treatment Questionnaire ¹⁷ | | X | | | | | |
| Analgesic Use Record ¹⁸ | | X | | X | | X | X |
| Adverse Events | | | | X | | | |
| Concomitant Medications | X | X | | X | | X | X |
| Telephone Call or Email ¹⁹ | | | | | X | | |

¹ All screening procedures must be completed \leq 28 days prior to surgery.

² This visit may be combined with Screening if all Pre-Operation visit procedures occur \leq 14 days prior to surgery. All pre-operation activities must be completed prior to starting study therapy.

³ All procedures must be completed prior to surgery.

⁴ Post-operation visit will occur 5 to 30 days after surgery.

⁵ Mid-radiation visit will occur 5-35 days after initiation of radiation therapy.

⁶ End of treatment visit will occur 1 to 30 days after the last treatment of radiation.

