10.3 End of Treatment

Upon discontinuation of study treatment, an End of Treatment visit will occur. The end of treatment visit will occur 1 to 30 days after the last radiation treatment or after patient discontinues treatment. For End of Treatment procedures see the Schedule of Events and the Assessments Section.

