16.4.4.1 MedWatch 3500A Reporting Guidelines

In addition to completing appropriate patient demographic (Section A) and suspect medication information (Section C & D), the report should include the following information within the Event Description (Section B.5) of the MedWatch 3500A form:

- Protocol number and title description

- Description of event, severity, treatment, and outcome if known
- Supportive laboratory results and diagnostics (Section B.6)
- Investigator's assessment of the relationship of the adverse event to each investigational product and suspect medication
- Expectedness of the event (i.e., expected or unexpected event).

16.4.4.2 FDA Reporting Timelines:

- 7 Calendar Day Report:

Any event that is fatal or life-threatening, unexpected, and definitely, probably or possibly related to study medication will be reported to the FDA by telephone or fax within seven calendar days of first learning of the event.

- 15 Calendar Day Report:

Any event that is serious, unexpected, and definitely, probably or possibly related to study medication will be reported to the FDA in an IND safety report within 15 calendar days of first learning of the event.

In accordance with 21 CFR 312.32, an Analysis of Similar Events should be included in the IND Safety Report. All safety reports previously filed by the investigator with the IND concerning similar events should be analyzed and the significance of the new report in light of the previous, similar reports commented on.

FDA fax number for IND Safety Reports:

Fax: [name]

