16.4.5 IRB Notification

The University of Utah IRB requires any unanticipated problems that may increase the risk to research participants be promptly reported. All study-therapy related, unexpected adverse events whose nature, severity, or frequency is not consistent with either:

- The unknown or foreseeable risk of adverse events that are described in the protocol related-documents, such as the IRB-approved research protocol, applicable investigator brochure, the current IRB-approved informed consent document, and/or other relevant sources of information, such as product labeling and package inserts; or
- The expected natural progression of any underlying disease or condition of the subject(s) experiencing the adverse event.

Adverse events meeting this criterion must be promptly reported to the IRB within 10 business days of awareness.

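### The two death-reporting clauses in section 16.4.2 do not meet: up to 29 days after an early end-of-treatment visit fall in neither, and other sections cover them only in part

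*Combined protocol and SAP*

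**What the plan says.** Section 16.4.2 has one sentence on deaths, with two clauses.

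- Clause 1, all causes: "Any death from any cause while a patient is receiving treatment on this protocol or up to the end of treatment visit".
- Clause 2, related deaths only: "any death which occurs more than 30 days after protocol treatment has ended but which is felt to be treatment related, must be reported".

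The visit that closes clause 1 has a movable date. Table 4, footnote 6, says: "End of treatment visit will occur 1 to 30 days after the last treatment of radiation". Section 10.3 adds a second starting point: "The end of treatment visit will occur 1 to 30 days after the last radiation treatment or after patient discontinues treatment".

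General safety collection closes at the same visit. For SAEs, section 16.4.2 has collection "end at the end of treatment visit or until a new cancer treatment is initiated, whichever happens the soonest". For AEs, section 16.4.1 says: "Collection of adverse events will begin from the first dose of study medication and until the end of treatment visit".

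Three other provisions bear on late deaths.

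- Section 16.4.4.2, seven-day report: "Any event that is fatal or life-threatening, unexpected, and definitely, probably or possibly related to study medication will be reported to the FDA".
- Section 16.4.5, on related and unexpected events: "Adverse events meeting this criterion must be promptly reported to the IRB within 10 business days of awareness".
- Section 16.4.3 requires follow-up reports on an SAE until it resolves, and passes follow-up information to the DSMC through the research compliance office.

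**The concern.** Clause 1 ends on a date that varies by patient, while clause 2 starts on a fixed day. Unless the visit falls on day 30 or later, there are days that neither clause names. The order is also odd. A related death on day 31 must be reported, but a related death on day 20 after a day-5 visit is not named, although it lies closer to treatment.

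This is a stated rule with a misplaced boundary, not a missing detail. At stake is whether the medical monitor and the DSMC see every death in the month after treatment. There is also a comparability problem: how long a patient's death counts as reportable depends on when the visit was booked, so deaths are ascertained over unequal windows.

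**Working it through.** The plan states no figure to reproduce. The check sets intervals side by side.

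**Inputs**

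- Visit day v, counted from the end of treatment: 1 to 30 (Table 4 footnote 6; section 10.3).
- Clause 1 covers deaths through day v (16.4.2).
- Clause 2 covers related deaths from day 31 (16.4.2).
- SAE collection covers nothing after day v (16.4.2).

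**Step 1: size of the gap.** Assume the visit and the 30-day clock start from the same date. This fits a patient who takes study drug to the last radiation session, as section 7.1 and Table 4 footnote 15 intend, or whose visit is timed from discontinuation under section 10.3. The days in neither clause run from v + 1 to 30, so gap = 30 − v.

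| Visit day v | Days in neither clause | Length |
|---|---|---|
| 1 | 2 to 30 | 30 − 1 = 29 |
| 5 | 6 to 30 | 30 − 5 = 25 |
| 14 | 15 to 30 | 30 − 14 = 16 |
| 30 | none | 30 − 30 = 0 |

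**Step 2: when the clocks differ.** Suppose study drug stops s days before the last radiation treatment, the visit is timed from radiation, and protocol treatment is read as study drug. The visit then falls s + v days after protocol treatment, and the gap is the larger of 0 and 30 − (s + v). With illustrative values s = 30 and v = 10, the visit is on day 40 and there is no gap.

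**Step 3: what the other provisions reach.** Consider a death after the visit and no later than day 30.

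| Kind of death | Explicit duty |
|---|---|
| Outcome of an SAE already reported | Yes: follow-up under 16.4.3, which reaches the DSMC |
| Related and unexpected, onset after the visit | Yes: FDA (16.4.4.2) and IRB (16.4.5) |
| Related but expected, onset after the visit | None |
| Unrelated, and not the outcome of an SAE already reported | None |

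The third row is a real possibility. Section 3.1.4 already describes serious gastrointestinal bleeding, ulceration and perforation, so a fatal gastrointestinal bleed that begins after the visit may be classed as expected.

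**The case against.** The strongest reply is that the safety system should be read as a whole. The FDA and IRB provisions carry no end date, and a known SAE is followed until it resolves. A reader might infer from section 16.4.2 alone that no treatment-related death in the gap need be reported. The documents do not support that, because the first two rows of the second table are covered. Nor do they support saying that the DSMC would never receive such a death: a fatal outcome of an earlier SAE does reach it.

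That reply narrows the point but does not remove it. The FDA and IRB routes apply only to events that are both related and unexpected. They also depend on the investigator learning of the death after collection has closed. The FDA text is written in IND safety-report terms, although section 16.8 says the study is IND exempt. The route to the medical monitor and the monthly DSMC meeting is SAE reporting under section 16.4.3, which the gap bypasses for a death with new onset.

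It can also be argued that section 16.4.2 requires every toxicity meeting the serious definition to be reported, related or not. But that sentence sits under a collection window that ends at the visit. If it had no time limit, clause 2 would be unnecessary.

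A further objection is that the gap does not depend on the visit date alone. This stands: Step 2 shows that it shrinks or disappears when study drug stops well before a visit timed from radiation.

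Finally, a reader might infer that these weeks are when a late drug-related cardiovascular or gastrointestinal death is most plausible. Nothing in the documents shows this, and the point does not need it.

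**Conclusion.** The point holds as a boundary error in section 16.4.2. The gap is 30 − v days, at most 29, for a patient whose visit is timed from the end of protocol treatment. Twenty-nine days is the worst case permitted, not a typical value, because the documents give no distribution of visit dates. For patients who stop study drug early and are seen after radiation, the gap may be smaller or absent, depending on what protocol treatment means, which section 16.4.2 does not say.

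Two classes of death in the gap have no explicit reporting duty and no required route to the medical monitor and DSMC: related but expected deaths with onset after the visit, and unrelated deaths that are not the outcome of an SAE already reported. How the first class is handled depends on the expectedness judgement.

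The primary endpoint is unaffected. The stopping rule in section 12.3 counts grade 3 or higher related toxicities that lead to discontinuation, so the case does not rest on that rule either. The change should be made because it concerns the reporting of deaths and is cheap.

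**What to change.** Rewrite the death sentence in section 16.4.2 to require reporting of:

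- any death, whatever the cause, from first dose through the later of the end-of-treatment visit or 30 days after protocol treatment has ended, with protocol treatment defined here as study drug; and
- any death after that point that is felt to be treatment related.

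Add that this rule applies even though other SAE collection ends at the visit.

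With this wording the all-cause clause runs to the larger of v and 30, and the related-death clause starts immediately afterwards, so the gap is 0 for every permitted v. The later-of wording matters. A plain 30-day limit would lose deaths that are reportable now: in the Step 2 example, an unrelated death on day 35 comes before the day-40 visit and is covered today. Changing only clause 2, so that it starts at the visit, would close the gap for related deaths alone.

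The cost is one sentence, plus a day-30 vital-status check by chart or telephone for patients whose visit came earlier. No dose, visit schedule or clinical rule changes.

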16.4.3 Reporting Serious Adverse Events

All serious adverse events should be reported as soon as possible but no later than one business day after the Investigator becomes aware. All SAEs must be reported via the HCI CTMS (OnCore) and submitted to [contact]. The HCI Clinical Site Monitor will in turn, submit the report to the Medical Monitor. The RCO will summarize and present all reported SAEs according to the Data and Safety Monitoring Plan at the monthly DSMC meeting.

At a minimum, initial SAE reports must include a description of the event, assessment of event causality, event grade, and the expectedness of the event. Although the Investigator may not know all the information at the time of the event, the available information should be reported. An SAE follow-up may be submitted at a later date once more information is known. It is required that follow-up reports be submitted until the SAE is resolved.

Follow-Up Information

It is recommended that follow-up reports be submitted as new information becomes available, however, a follow-up report should be submitted within 7 days of knowledge of event resolution. Follow-up information will be added to the SAE in OnCore and submitted to the DSMC via RCO.

